**PROTOCOL SYNOPSIS**

Protocol Title	Full Scale Randomized Trial of an Innovative Conversational Agent for Smoking Cessation (QuitBot)
Protocol Number	10359
Protocol Sponsor	NCI, NIH
Trial Phase	III
Trial Type	Randomized clinical trial
Study Objectives	To determine the effectiveness of a digital conversational agent for smoking cessation; specifically, to conduct a randomized controlled trial of QuitBot (n = 823) versus SmokefreeTXT (SFT) (n = 823), in order to determine whether QuitBot provides higher quit rates than SFT.
Study Design	2-arm parallel group randomized trial
Population	1647 adult male and female daily smokers who currently smoke and want to quit smoking in the next 30 days
Primary Endpoints	30-day biochemically confirmed cigarette smoking cessation at 12 months after randomization
Secondary Endpoints	30-day biochemically confirmed cigarette smoking cessation at 3 and 6 months after randomization
Investigation Device	QuitBot conversational agent (CA)
Type of control	Active (SmokefreeTXT text messages)
Trial Blinding	Participants and outcome assessors will be blinded
Treatment Groups	Intervention, Control
Assessments	Follow-up assessments at 3, 6, and 12 months
Number of trial subjects	1647
Estimated duration of trial	30 months
Duration of Participation	12 months

**ABBREVIATIONS**

CA	Conversational agent
RCT	Randomized Clinical Trial
SFT	SmokefreeTXT
App	Smartphone application
NLP	Natural language processing
QALY	Quality-adjusted life years

TLS	Transport Layer Security
MS	Microsoft
LUIS	Language Understanding Intelligence Service

## 1.0 GENERAL INFORMATION

This document is a clinical research protocol and the described study will be conducted in compliance with the IRB approved protocol, associated Federal regulations and all applicable IRB requirements.

**Rationale:** Cigarette smoking accounts for 480,000 premature deaths and one third of all cancer deaths annually in the US. There is enormous need for high-impact, cost-effective population-level interventions for smoking cessation. For the past 15 years, mobile phone-delivered text messaging interventions such as the NCI's SmokefreeTXT (SFT) have been a prominent technology addressing this need. However, very much like all widely available technologies for smoking cessation (e.g., websites), text messaging interventions have modest quit rates, driven largely by low engagement. Fortunately, a new technology provides a therapeutic conversation to address the problem of engagement that impacts text messaging and other current digital technologies for smoking cessation. Advances in machine learning, natural language processing, and cloud computing are now making it possible to create and widely disseminate conversational agents (Cas), which are computer-powered digital coaches designed to form long-term social-emotional connections with users through conversations. Cas are supportive, empathic, reflectively listen, provide personalized responses, and offer goal setting and advice appropriately timed to the needs of the user. Regarding Cas for smoking cessation, the major knowledge gaps are: (1) their efficacy, (2) theoretical mechanisms, and (3) the cost-effectiveness. Also unexplored are the potential baseline moderators of Cas for smoking cessation. We recently developed a CA for smoking cessation, called "QuitBot," evaluated it in a diary study, and then tested it in a pilot randomized controlled trial (N = 306), comparing it with the NCI's SFT. The pilot RCT design was very feasible with 93% three-month follow-up. QuitBot had: (a) high participant engagement and (b) high quit rates at the three-month follow-up—very promising in comparison with SFT.

**Objectives:** Addressing these knowledge gaps and building on the promising results of our QuitBot research, the project will conduct a randomized controlled trial of QuitBot (n = 823) versus SmokefreeTXT (n = 823) with 12-month follow-up in order to determine whether QuitBot: (1) provides higher quit rates than SFT, (2) has smoking cessation outcomes significantly mediated by therapeutic alliance processes and engagement, and (3) is cost-effective vs. SFT. In addition, this study will explore whether these baseline factors moderate the effectiveness of QuitBot: trust, social support, and demographics (e.g., sex). This innovative project will advance the fields of research on Cas both for smoking cessation in particular and for health behavior change in general—regardless of whether the results are positive or null. Positive results could have high population-level impact and stimulate new lines of research into CA dissemination and implementation, and the adaptation of Cas for multiple subpopulations of smokers, languages, and community and medical settings.

**Phase:** Phase III RCT.

**Methods:** Randomized controlled trial of QuitBot (n = 823) versus SmokefreeTXT (n = 823) with 12-month follow-up.

### 1.1 Protocol Title

Full Scale Randomized Trial of an Innovative Conversational Agent for Smoking Cessation (QuitBot)

### 1.2 Sponsor Information

NCI, NIH

## 2.0 INTRODUCTION TO THE PROTOCOL

### 2.1 Introduction

Text messaging, very much like all widely available technologies for smoking cessation (e.g., websites and smartphone apps), have modest quit rates driven largely by low user engagement [1, 2, 16-21]. Needed now is an intervention model

that can fundamentally shift beyond text messaging and other digital technologies in order to boost user engagement and thereby increase quit success rates.

A new technology provides a therapeutic conversation to address the problem of engagement that impacts text messaging and other current digital technologies for smoking cessation. Advances in machine learning, natural language processing, and cloud computing are now making it possible to create and widely disseminate conversational agents (CAs), which are computer-powered digital coaches designed to form long-term social-emotional connections with users through conversations [22, 23]. Interactions are tailored to the users' unique challenges and barriers to quitting smoking. CAs are supportive, empathic, reflectively listen, provide personalized responses, and offer goal setting and advice appropriately timed to the needs of the user. In addition, CAs have 24/7 availability, absence of judgement, and the ability to quickly calculate and thereby show results and measure progress [24, 25]. CAs are potentially less costly for users than text messaging because they do not require a paid cellular plan. Instead, CAs only need a Wi-Fi or other internet connection. CAs are available anytime and have potentially high population level reach.

Regarding CAs for smoking cessation, the following are unknown: (1) their efficacy, (2) theoretical mechanisms, and (3) the cost-effectiveness. Also unexplored are the potential baseline moderators of CAs for smoking cessation.

## 2.2 Preclinical Data

[name] obtained NCI pilot funding (CCSG Y43 Pilot from NCI P30CA015704) to develop and pilot test a CA for smoking cessation. After developing the QuitBot CA using content analysis, user-centered research, and prototype testing, we conducted a diary study to obtain ongoing feedback on users' interactions with QuitBot, its design, and content. In user-centered design research, a diary study of two weeks with 6 to 12 participants is recommended to obtain this initial feedback [81, 82]. Accordingly, we conducted a single arm 14-day diary study of the program with 9 adults who were smoking at least daily (all smoked 30+ cigarettes/day), interested in quit smoking, and recruited from around the US via Facebook ads. Four were chosen because they were skeptical about CAs being able to help someone quit smoking. All nine participants completed: (1) the 60-minute video-based orientation, (2) 14 evening diary entries (15 minutes each) about their interactions with QuitBot, its design, and content, (3) on day seven, a 15-minute video-based check-in call on their impressions to date, and (4) a 60-minute video-based exit interview. The results showed that, even though the focus was on usability, by day 14, three participants quit smoking and all remaining six reduced to 3-4 cigarettes per day. Ratings for usefulness, satisfaction, and likelihood of recommending to a friend were all very high: 4.33, 4.67, and 4.88 on a 0 (not all) to 5 (extremely) scale. All nine felt highly supported by the QuitBot CA. They liked the skills training for coping with urges and lapses. Their feedback yielded minor content edits and fixes of technical bugs.

## 2.3 Clinical Data to Date

We recently conducted a multi-step design process that yielded a fully functional CA cessation intervention called QuitBot. Participants were highly receptive to QuitBot in our single-arm diary study. We then tested QuitBot in a pilot randomized controlled trial (N = 306), comparing it with the NCI's SmokefreeTXT. The pilot RCT design was very feasible with 93% three-month follow-up. QuitBot had: (a) high participant engagement and (b) high quit rates at the three-month follow-up. QuitBot participants expressed feeling engaged with and supported by the program.

Based on our successful methods for national recruitment [84], we developed and targeted FB ads with ongoing monitoring and adjustment of recruitment yield. These efforts yielded 1853 participants screened, 974 eligible, 452 consented, and 306 randomized (153 in each arm). Based on evidence from text messaging trials meta-analyses [1], we stratified randomization on biological sex (male vs. female), heaviness of smoking index score ( $\leq 4$  vs.  $>4$ ), and percent confidence in being smoke-free in 12 months ( $\leq 70\%$  vs.  $>70\%$ ). The two conditions were balanced at baseline on all measured characteristics (all p-values  $> .05$ ). Participants were mean age 36.3, 67% female, 28% minority, 52% unemployed, 43% high school or less education, 69% smoking at least half pack daily, and 59% high nicotine dependent. The characteristics of this FM sample are very similar to those of m/e-health trials [1, 2, 7]. To maximize outcome data completion, we followed our team's successful protocol [84]: four sequential survey modalities (first Web, followed by phone, mail, and postcard). Participants received \$25 for submitting their responses, and received an additional \$10 bonus for completing the Web survey within 24 hours. The achieved outcome survey completion rate of 93%, provided confidence in the follow-up survey methods. The data retention did not differ between study arms ( $p = .374$ ). For example, the point estimate for the number of days from randomization to the last user input showed that QuitBot participants engaged 26.3 (95% CI: 19.7, 33.0;  $p < .001$ ) days longer than SFT participants. QuitBot's intervention completion results are substantial when considering that each day's content involves a 3 to 5-minute conversation. The 30-day point prevalence (missing=smoking) abstinence rates at three-month follow-up (primary outcome) were 32% for QuitBot vs. 23% for SFT (OR = 2.18; 95% CI: 1.08, 4.39;  $p = .030$ ). Results for the secondary outcome of cessation from cigarettes and all other nicotine or tobacco products (except FDA-approved nicotine replacement) were promising.

Building on these promising results, a comparative effectiveness randomized trial with a fully-powered sample size (N = 1647) and longer-term follow-up (i.e., 12 months) is now needed to determine whether QuitBot: (1) provides higher quit rates than SmokefreeTXT, (2) operates according to therapeutic mechanisms of change, and (3) is cost-effective vs. SmokefreeTXT.

**Study Objectives:** Conduct a randomized controlled trial of QuitBot (n = 823) versus SmokefreeTXT (n = 823), in order to determine whether QuitBot:

Objective 1. Has significantly higher 30-day point prevalence abstinence at 12 months post-randomization than SmokefreeTXT. Importance of this objective: will determine both arms' quit rates with precision and whether the QuitBot provides more robust quit rates than SmokefreeTXT.

Objective 2. Has smoking cessation outcomes significantly mediated by therapeutic alliance processes and engagement indicators in a serial multiple mediator model. Importance of this objective: will show how CAs work and identify communication processes needing further targeting. This knowledge is valuable both for CA smoking cessation interventions in particular and CA behavior change interventions in general.

Objective 3. Will be cost-effective vs. SmokefreeTXT (SFT), as measured by cost per quitter, cost per life year gained, and cost per quality-adjusted life year (QALY) gained. Importance of this objective: will provide payors and policymakers an assessment of value to inform decisions about whether to adopt QuitBot.

**Exploratory Objective:** Explore whether these baseline factors moderate the cessation outcomes of QuitBot, as compared to SmokefreeTXT: (a) trust, (b) social support, (c) demographics (e.g., sex). Importance of this objective is to identify: (1) who benefits most so that they can be provided the intervention; (2) who benefits least so that future research can explore why and determine how best to improve the intervention for them.

**Impact:** This study will advance the fields of research on CAs both for smoking cessation in particular and for health behavior change in general—regardless of whether the results are positive or null. Positive results could have high population-level impact and stimulate new lines of research into CA dissemination and implementation, and the adaptation of CAs for multiple subpopulations of smokers, languages, and community and medical settings.

Sections on Study Agent, Dose Rationale, and Other Agents have been removed as not relevant since this is not a drug trial.

### **2.3.1 Intervention Development**

For the pilot, a version 1.0 of the QuitBot CA program was developed by the study staff in collaboration with Data Scientists in the Hutch Data Commonwealth (HDC) department. To create the greater technological complexity of incorporating more NLP for more sophisticated human-like conversational engagement, partnership with Data Scientist experts in Microsoft AI for Good, led by [name], joined study staff. Also, after further review of privacy and security considerations associated with Facebook Messenger, we opted to create our own smartphone app to host version 2.0 of the QuitBot CA program. This will allow for greater privacy protections for participant information and greater capacity for secure data collection.

## **2.4 Risks/Benefits**

### **2.4.1 Potential Risks.**

The main risk to participation in this study is breach of confidentiality.

A breach of confidentiality could possibly occur if, for example, an unauthorized person accesses the study's database records, QuitBot app records, text message log, and/or study hard copy records, or if telephone survey conversations are accidentally overheard by someone who does not know the participant smokes or is taking part in a smoking cessation study. Also, some participants might feel emotional upset during their assigned intervention or embarrassment when talking about their smoking during the telephone surveys. Finally, some smokers making quit attempts may experience some short-term discomfort associated with nicotine withdrawal.

Participants will be fully apprised of all anticipated risks in the informed consent and other intervention materials, and will have the option to opt out of the trial at any time.

### **2.4.2 Protection Against Risk**

**Protection against breach of confidentiality.** Our research group uses the following confidentiality procedures: All data records are stored in secured servers or in locked file cabinets inside locked (limited access) rooms in our secured building. Completed paper surveys have no identifying information other than the participant's unique Study ID number. Access to paper and electronic study data and records, and to the link between participant names and Study ID numbers, is restricted to a limited number of need-to-know study personnel, and data may not be taken off the premises for any purpose. Users have no access to project computers unless they have a domain (network) account. The electronic database resides on a server that is in a locked cabinet in a locked server room, with strictly limited, key-card access. The server also lies behind the Center's firewall, which permits no access to the server at all from outside the Center, except through the database server port using a secure, encrypted channel. The research group places additional restrictions, through DBMS software, on which data items users may view and the kinds of activities they are permitted. These permissions are based strictly on each staff member's need to see and use the data. No staff member will be able to access the data by default. The Project web server also resides in the same secure room as the database server, and is similarly protected by firewalls, with no user access except through the web server software. The database administrators maintain a rigorous system of daily full tape backups of the database and web servers. The backups include sets of tapes stored at a secure distant site.

Study participants will be recruited using a publicly accessible web site running on the Apache web server on a Linux operating system. Internal servers are made available outside the Hutch firewall directly via specific firewall allowances to connect to specific resources. After indicating interest in the study, participants will complete online surveys via HTTPS using Transport Layer Security (TLS). Employment of the TLS protocol will prevent anyone from intercepting data passed between the end user's web browser and the web server. All connections to the enrollment website will be made using TLS.

Surveys are implemented using a secure, metadata-driven system designed and tested by our software development team, which has been in use for the past five years for other research studies in which participants enter information about themselves. Surveys are hosted on a Web site running on the Apache web server on a Linux operating system. Study participants who complete these online surveys will only have access to data that they have entered on in-process surveys. Participants may access partially completed surveys via a participant-specific link provided by email and entry of the participant's birthdate. Once surveys are complete, the data are inaccessible from the web site. Participants and others will be prevented from accessing any other data on the Web server by a number of operating system, web server, and application controls. Users will connect to the web site to complete the surveys using the TLS protocol. Employment of the TLS protocol will prevent anyone from intercepting data passed between the end user's web browser and the web server.

The QuitBot CA is implemented within the Microsoft Bot Framework. The core bot logic is developed in Node.js using the Microsoft Bot Builder Software Development Kit (SDK). The code is compiled, hosted, and run as an App Service on a private Fred Hutch account on the Microsoft Azure cloud, which uses a Linux operating system. In the same cloud environment, relevant user data (e.g. users' current positions within the cessation dialogues, their predicted quit dates, etc.) is stored using Azure Table Storage. The CA utilizes the Microsoft Bot Connector to interact with the table storage, and to route messages (securely over Transport Layer Security [TLS]) to and from the frontend of the QuitBot CA, a custom smartphone application. The Bot Connector is tied directly to the Fred Hutch owned QuitBot application. After being randomized to the QuitBot arm, study participants will be sent a link enabling them to download and login to the QuitBot app and then interact with the QuitBot CA, as using the login verifies them as a valid, active participant. Once confirmation is received, QuitBot will begin serving cessation dialogue content to the participant, first by initiating contact (twice daily, at user-specified times) via proactive messaging, then by reactive responses to the participant's chat input. At multiple points throughout the cessation dialogues, the bot will utilize Microsoft's Language Understanding Intelligent Services (LUIS) to perform more detailed analysis on participants' messages, including categorical classification, identification of specific types of user responses, routing of conversations into specific topics, etc. This LUIS service will also be hosted within Fred Hutch's Azure cloud environment, and integrated with the Bot Framework via Azure Bot Services. The QuitBot CA intervention app will be accessed via password-protected login any time after randomization. The analytics database for the CA (which automatically records participants' utilization of the CA) will be located on a Microsoft Azure server that is integrated into the Center network and is protected by a firewall. The analytics database firewall permits no access to the server at all from outside the Fred Hutch, except through the database server port using a secure, encrypted channel. We will inform participants: (1) we are recording their utilization of their assigned intervention only for research purposes, (2) where their utilization data is stored and how it is transmitted, and (3) the nature of the data encryption.

The SmokefreeTXT text messaging program is hosted by ICF, a consulting services company contracted with the Federal government to manage the program. ICF provided [name] with a copy of the SmokefreeTXT message library for the QuitBot pilot trial, and study programmers host it on a secure server behind the Fred Hutch's firewall, which has the same

access restrictions and backup system as the database server described above. Text message delivery will occur through Nexmo SMS API, which is also used to send study survey reminders.

**Protection Against Emotional Upset or Embarrassment.** If participants feel uncomfortable answering research questions or participating in their assigned intervention they will be able to skip any assessment items that they are not comfortable answering. Participation during the intervention will also be voluntary. Participants may choose not to participate in any components of their assigned intervention which make them feel uncomfortable. All participants will have the option of contacting via email the PI, [name], a Licensed Clinical Psychologist with the experience and expertise to responding effectively to potential adverse emotional reactions. He will plan to respond within 24 hours. If a referral to treatment is needed, he is acquainted with appropriate referral facilities and processes of identifying treatment available throughout the United States. Furthermore, the QuitBot is programmed to respond to any mention of "suicide" and self-harm keywords by referring the participant to the National Suicide Prevention Lifeline number and by confidentially alerting the study staff and [name].

**Protection Against Discomfort of Nicotine Withdrawal.** Participants who quit smoking may experience some discomfort associated nicotine withdrawal. Participants will also be fully informed of the symptoms of nicotine withdrawal during the informed consent process. Interventions in both treatment groups provide strategies designed to cope more effectively with symptoms of nicotine withdrawal. Finally, participants in both treatment groups will be given information on pharmacotherapy for smoking cessation (e.g., nicotine patch) and how to obtain these medications.

**Reporting Breaches and Complaints.** Taken together, these measures will minimize risks to study participants. However, should a breach/complaint occur, or if a participant is not pleased with any of the surveys or with the study's procedures, the study's scientific staff will attempt to address the concerns. The breach/complaint will be reported to the IRB office, and the participant will be referred to the Fred Hutch IRO Director. If a security breach should occur, the study team will notify participants and the IRB office.

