## 4.0 SAFETY CONSIDERATIONS

### 4.1 Stopping Rules

#### 4.1.1 Stopping Rules for the Individual Participant

We have an established protocol in place with a referral policy for the clinical management of these participants with active suicidal/homicidal ideation.

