Smokefree comparison intervention: for initial evidence of whether CA is a fundamental shift beyond text messaging, SmokefreeTXT (SFT) is the ideal comparison. A 42-day program, SFT is the most widely accessible text messaging program in the US. It is non-proprietary and free to the public, thereby providing maximal accessibility and replicability. Daily messages are sent about the importance of quitting smoking, setting a quit date, preparing to quit, quitting, and maintaining abstinence. Daily messages check in about quit status. Three keywords can be sent by users to receive anytime help: “CRAVE” (on how to cope with urges), “MOOD” (on how to cope with moods triggering smoking), and “SLIP” (on how to cope with lapses). See Figure 3 for sample message. NCI’s SFT contractor (ICF International) provided us the full content of SFT so that we could internally host a secured private version for research. For blinding, the intervention was called “QuitBot.” Comparisons between QuitBot and SFT are shown in Table 2. In both SFT & QuitBot, participants receive two prompts per day (three on the quit day), with those not responding to prompts continuing where they left off.

[figure not shown]

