## 8.0 ADVERSE EVENTS

### 8.1 Adverse Event

According to ICH guidelines (Federal Register. 1997; 62(90):25691-25709) and 21 CFR 312.32, IND Safety Reports, and ICH E2A, Definitions and Standards for Expedited Reporting, an adverse event is defined as follows:

An adverse event is any untoward medical occurrence in a clinical investigation subject administered a medicinal product and which does not necessarily have a causal relationship with this treatment. An AE can therefore be any unfavorable and unintended sign (including an abnormal laboratory finding), symptom, or disease temporally associated with the use of a medicinal product, whether or not considered related to the medicinal product.

Abnormal laboratory values for laboratory parameters specified in the study should not be recorded as an adverse event unless an intervention is required (repeat testing to confirm the abnormality is not considered intervention), the laboratory abnormality results in a serious adverse event or the adverse event results in study termination or interruption/discontinuation of study treatment.

Medical conditions present at screening (i.e., before the study treatment is administered) are not adverse events and should not be recorded on adverse event pages of the CRFs. These medical conditions should be adequately documented on the subject chart. However, medical conditions present at baseline that worsen in intensity or frequency during the treatment or post-treatment periods should be reported and recorded as adverse events.

For this trial, an example of an unexpected event that is not adverse is a participant who has become very unhappy with trial procedures. Adverse events (AEs) are any untoward occurrence with a trial participant whether or not it can be considered to be related to their smoking cessation intervention (the QuitBot CA or SmokefreeTXT programs). An example of an adverse event in this trial could include an increase in depressive symptoms. Serious adverse events (SAEs) include any AE that results in death, a real risk of dying, inpatient hospitalization, persistent or significant disability/incapacity, or AEs that require intervention to prevent permanent impairment or damage. In this trial, an example of a serious adverse event would be a suicide attempt.

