**QuitBot CA utilization data and security.** The QuitBot CA program will be accessible to participants when they access the download and login link sent to them in their secure trial enrollment email. During the enrollment process, participants check their smartphone storage requirements and opt-in to download the app. If the participant is then randomized to the QuitBot arm, a randomly-generated opt-in ID is sent to the QuitBot backend, where it is whitelisted and connected to their user data, which allows them to fully interact with the bot content. Non-whitelisted users who attempt to download the app will not be able to login and will receive a single generic response, redirecting them to the study website page for more information. The CA will collect information on participants' responses to the program, including triggers to smoke (physical, emotional, and situational triggers), motivations to quit, barriers to quitting, and number of cigarettes smoked in end-to-end encrypted "private conversations", and it will not collect PHI. Data will also be collected on usage information: the number of days user interacted with assigned intervention and whether users completed assigned intervention. This information will be extracted over a secure connection on a weekly basis, and stored on a secure internal Fred Hutch server. A raw copy of the data serves as an additional backup beyond the ongoing built-in Azure storage backup processes. An automated script creates a fully de-identified and cleaned copy of the data, to send to the study team analysts. This usage data can be tied to the survey data using the aforementioned randomly generated opt-in IDs.

**SmokefreeTXT utilization data and security.** Participants randomized to the SmokefreeTXT arm will be asked to provide a quit date on a website with data transmission via Transport Layer Security (TLS.) A schedule of text messages is set up based on the quit date. Participants can request that messages be stopped at any time. Date stamps and content of the outgoing messages and incoming messages with participant responses to queries about mood, cravings, relapse, and smoking status will be stored on secured Fred Hutch servers. These data will only be accessible to Fred Hutch Shared Resource programmers and not accessible via websites. The programmers will prepare de-identified utilization data for analysis.

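### The automatic self-harm keyword response is described for QuitBot only; nothing equivalent is described for incoming SmokefreeTXT messages

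*Combined protocol and SAP*

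**What the plan says.** The combined protocol and SAP deals with distress in section 2.4.2, in the paragraph on emotional upset or embarrassment. One safeguard there is open to everyone: "All participants will have the option of contacting via email the PI". The next is tied to one program. It begins "Furthermore, the QuitBot is programmed to respond to any mention of" suicide and self-harm keywords, and the response is made "by referring the participant to the National Suicide Prevention Lifeline number and by confidentially alerting the study staff".

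Section 7.0 describes how SmokefreeTXT handles incoming texts: "Three keywords can be sent by users to receive anytime help". The three are CRAVE, MOOD and SLIP. Section 10.1 adds that "incoming messages with participant responses to queries about mood, cravings, relapse, and smoking status will be stored on secured Fred Hutch servers", and then: "These data will only be accessible to Fred Hutch Shared Resource programmers and not accessible via websites".

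Two further statements bear on the point. Section 4.1.1 says: "We have an established protocol in place with a referral policy for the clinical management of these participants with active suicidal/homicidal ideation". Section 8.1, having named a rise in depressive symptoms as an example of an adverse event, says: "In this trial, an example of a serious adverse event would be a suicide attempt".

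**The concern.** Both programs receive messages from participants, and both touch on mood. Only one is described as watching those messages for self-harm and acting at once. The plan itself treats worsening depression and suicide attempts as events that could occur in this trial, so a disclosure in a text reply is a foreseeable case.

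What is at stake is mainly participant safety: whether someone in the comparator arm who texts about self-harm gets a crisis number and comes to the attention of staff. A smaller matter is safety reporting. If one arm has a detection route that the other lacks, self-harm events listed by arm are hard to read unless the report says how each one came to light.

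**Working it through.** The plan states no figure on this point and no arithmetic applies. The check is a comparison of what is described for each arm.

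**1. Does the 2.4.2 rule cover both arms?** Section 7.0 says the comparator was given the QuitBot name for blinding, so the word could be ambiguous. In 2.4.2 and 10.1, however, QuitBot means the conversational agent, and SmokefreeTXT is named separately. Section 2.4.2 also signals when a protection is shared: the email option is for all participants, and the withdrawal protections refer to both treatment groups. The keyword rule carries no such signal. It reads as belonging to the conversational agent.

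**2. Could a SmokefreeTXT participant disclose self-harm in a message?** Yes. Section 10.1 says that incoming messages include answers about mood and relapse, and section 7.0 lets users text MOOD at any time.

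**3. Could the SmokefreeTXT system act on such a message?** Probably. Sections 2.4.2 and 7.0 say the study hosts its own copy of the program, and that copy already responds to three keywords. Whether it can search free text for a longer list is not stated.

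**4. Do the shared safeguards fill the gap?** Taken in turn:

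- Email to the PI (2.4.2): the participant must start the contact.
- Referral policy for active ideation (4.1.1): not limited to an arm, but no means of finding the participant is given.
- Staff reporting of adverse events (8.1, 8.5): runs through recruitment, intervention and follow-up, and so includes the telephone survey contacts in 7.2. It starts once a staff member knows of something. The plan expects about 92% of survey completers to respond online, so most would have no such call.
- Monthly reports and review (8.5, 9.0), the twice-yearly investigator review (9.0) and committee review at least annually (9.0): these consider what has already reached staff.

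None of these is described as acting on message content.

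**5. Result.** One automatic response to message content is described, for QuitBot. None is described for SmokefreeTXT.

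**6. Can the consequence be sized?** No. The documents give no reply rate, disclosure rate or alert count for either arm.

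**The case against.** The strongest reply is that this argues from silence. The limit on who can open SmokefreeTXT messages is a storage and confidentiality statement. An automatic rule runs in code and needs no human reader, so the limit does not show that no rule exists. The QuitBot storage paragraph in 10.1 does not mention the QuitBot alert either, and the operating detail of the referral policy in 4.1.1 lies outside this document. All of this stands. A reader might infer that SmokefreeTXT messages go unscreened, or that the comparator arm is unprotected. The documents support neither: they show only that no rule is described, and they do describe safeguards open to both arms.

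A second reply is that the difference follows from the interventions. QuitBot holds daily conversations and answers natural language, so it needs a rule for what to say when self-harm comes up. SmokefreeTXT sends scheduled messages and was chosen because it is a freely available, replicable public program; a crisis response would alter it slightly. This is a plausible reason for where the rule sits, but the plan does not give it, and SmokefreeTXT also asks about mood.

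A third reply is that no planned result depends on this. That is correct. Section 11 sets out no between-arm test of adverse events. Under section 8.4 the PI, with the co-investigators and project manager, decides whether an unexpected event counts as an adverse event, so a flagged message is not one by itself. A reader might infer that self-harm counts will be biased towards QuitBot. That is a possibility, not a finding.

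**Conclusion.** The point holds as a minor one about participant safety. If the plan is followed as written, a SmokefreeTXT participant who mentions self-harm in a message has no described automatic Lifeline referral or staff alert, and a QuitBot participant does. The primary analysis is unaffected. Any difference in detection between the arms cannot be quantified and may be zero.

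The conclusion rests on two assumptions: that QuitBot in 2.4.2 means the conversational agent, which the surrounding text supports, and that the document describes the automatic safeguards in use. If SmokefreeTXT replies are already screened, the point reduces to a missing sentence. How much a live rule can still do is uncertain. Section 3.4 records accrual of 1647 and section 7.1 gives 42 days of content, so the programs may have ended or be close to it, although participants who do not respond resume where they stopped and may run longer.

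**What to change.** While any participant is still in the program, apply the QuitBot keyword list, Lifeline reply and confidential alert to incoming SmokefreeTXT messages. Send the alerts to staff who do not collect outcomes, because section 7.2 keeps the survey unit blind to assignment. If this is already done, say so in 2.4.2.

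If self-harm events are reported by arm, report how each was detected (keyword alert, email to the PI, telephone contact or other), so that events found by a route active in one arm only can be recognised. This applies even if the programs have ended.

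The cost should be small: one more keyword rule on a message stream that the study already hosts, and a sentence in 2.4.2. It assumes that the system can search free text and that staff can answer alerts promptly; the documents confirm neither. The downsides are a few more alerts to handle, a small addition to the comparator, and limited reach if few or no participants are still in the program.
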